10.4 Data transformations

Due to the nature of the analysis of the primary and secondary endpoints, it is not expected that any of the data will have to be transformed.

10.5 Multicentre Studies

This is a multi-center clinical study, with standardization of subject enrolment, data entry and adverse event reporting. All investigational sites will follow the requirements of a common protocol, data collection procedures and forms.

Given the nature of the intervention, patients from different centers are assumed to be exchangeable. An exploratory analysis will estimate the variation in the primary outcome between centers, adjusting for the different case-mix of patients, though the precision of this estimate is expected to be low.

10.6 Multiple Testing

Since the primary analysis for performance is based only on one endpoint (i.e. revascularization based on the mTICI score), no multiple comparisons will be necessary.

10.7 Planned Subgroups, Interactions, and Covariates

Subgroup analyses will be performed within the ITT population and the TS on outcomes specific to each subgroup analysis. A summary of the proportions of subjects, along with their 95% confidence intervals, within each subgroup for both the primary efficacy outcome and the primary safety outcome, will be reported. Secondary endpoints (see 5.2.3) will be examined descriptively across these subgroups where relevant to further advance the safety and efficacy profile of the device.

A listing of all subgroup analyses to be carried out is provided below with the outcomes listed for each subgroup analysis:

Table 3: Subgroup analysis listing

Analysis	Outcomes	Notes
Males vs. Females	
• Primary efficacy• Primary safety	
Compare results for the 21mm length devices to those associated with 33mm devices	
• Primary efficacy• Primary safety• Good clinical outcome (mRS)	See 13.4.1

Analysis	Outcomes	Notes
Compare outcomes from the product codes (ET 008 & ET 007) vs. (ET 008-21 & ET-007-21) vs. (ET 008-33& ET 007-21)	
 • Primary efficacy • Primary safety • Adverse Effects 	See 13.4.2
Specific vascular location of the occlusion (i.e. proximal M1/ distal M1 /M2, etc.)	Primary efficacy	
Locations to be grouped as follows:
 
 • ICA • ICA Terminus (L or T-type) • MCA M1 • MCA M2 • Vertebral • Basilar
Compare use of a balloon guide vs. no balloon guide	Primary efficacy	
Compare use of an intermediate catheter vs. no intermediate catheter	Primary efficacy	
Compare outcomes of patients recruited under revision 03 (issued 19th June 2015) to those under revision 05 (issued 28th June 2016)	Primary efficacy	See 13.4.3
Patients with severe hypertension at enrolment (defined as patient with either SBP>220 mmHg or DBP>120 mmHg) compared to those without.	Primary efficacy	

Demographic and baseline characteristics, procedural information, and clinical outcomes (efficacy and safety) will also be summarized.

10.8 Sensitivity Analysis

A set of sensitivity analyses will be carried out to assess the robustness of conclusions to varying definitions of the target population, definitions of endpoints, and treatment of missing data. These are listed below, along with the relevant outcome to be analysed for each sensitivity analysis. Analyses will report summary parameters (mean or proportion) along with the 95% confidence interval for each.

Analysis will follow the procedure of 10.7 and are listed in the table below.

Table 4: Sensitivity analysis listing

Analysis	Outcomes	Notes
Re-definition of outcomes under rescue therapy	
 • Primary efficacy • Good clinical outcome (mRS) • Neurological deterioration 	Re-analysis of outcomes treating observations with rescue therapy as: 1. observed and, 2. for the secondary outcomes; Clinical outcome and Neurological deterioration, as failure to achieve success
Exclusion of rescue therapy population	Primary efficacy	Re-analysis only on participants not having rescue therapy
Treated Set	Primary efficacy	Re-analysis of outcome using different population according to eligibility criteria (See 9.1)
mITT analysis	Primary efficacy	Re-analysis of outcome using different population according to eligibility criteria (See 9.3)

Analysis	Outcomes	Notes
Redefinition of rescue therapy	Primary efficacy	Re-analysis of outcome given wider definition of rescue therapy to include use of all thrombolytic drugs

10.9 Derived and Computed Variables

The following derived and computed variables have been initially identified. It is expected that additional variables will be required. The SAP will not be amended for additional variables that are not related to the primary target or key secondary target variables. Any additional derived or computed variables will be identified and documented in the code that creates analysis files.

1. Primary safety endpoint:

Rate for subject i: $sICH_i + (SADE_i - SADE_{sICH(i)})$, where:

$sICH_i$ = the number of occurrences subject 'i' has of Symptomatic Intracerebral hemorrhage ($sICH$) within 24 hours (-8/+12 hrs) post-procedure

$SADE_i$ = any other Serious Adverse Device Effects subject 'i' has

$SADE_{sICH(i)}$ = Serious Adverse Device Effects subject 'i' has which are already counted in $sICH_i$

2. Procedure Time – derived by calculating the time from when the groin was punctured until the acquisition time for the final post treatment confirmation of result angiography (i.e. the time from groin puncture to acquisition of the final angiographic images).

$Time_{final\ post-treatment\ visualization\ of\ final\ angiography\ result} - Time_{groin\ puncture}$

3. Time to treat - derived by calculating the time from angiographic visualization of the large vessel occlusion to the first time TICI 2b or greater was recorded angiographically, or if TICI 2b or greater was not achieved, the time of last angiographic result.

If $\geq mTICI\ 2b$ achieved:

$Time_{\geq mTICI\ 2b\ achieved} - Time_{min(time\ of\ angiographic\ visualization\ of\ the\ large\ vessel\ occlusion)}$

If $\geq mTICI\ 2b$ not achieved:

$Time_{max(time\ of\ angiographic\ result)} - Time_{min(time\ of\ angiographic\ visualization\ of\ the\ large\ vessel\ occlusion)}$

4. Modified Intention to Treat population:

Only patients who are contra-indicated for IV-tPA or in whom IV-tPA has failed will be included (Failure of IV-tPA is defined as angiographic evidence of persistent target vessel occlusion, one hour or more after the initiation of IV-tPA therapy).

This is derived by calculating the difference between the time of the angiography confirming occlusion before first pass and the time of IV-tPA initiation.

$Time_{angiography\ confirming\ occlusion\ before\ first\ pass} - Time_{IV-tPA\ initiated}$

11 Study Subjects

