3.1 Primary endpoint

The primary efficacy endpoint of the study is revascularization measured using modified Thrombolysis in Cerebrovascular Infarction (mTICI inclusive of the 2c rating). Successful achievement of the endpoint is defined as achieving a mTICI score of 2b or greater in the target vessel, following 3 or less passes of the EmboTrap device.

The primary safety endpoint will be measured as the occurrence of Symptomatic Intracerebral hemorrhage (sICH) within 24 hours (-8/+12 hrs) post-procedure, together with any other Serious Adverse Device Effects (excluding those already counted in sICH).

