The modified TICI (mTICI) result for assessing the primary efficacy endpoint for a subject will be taken from the final core laboratory adjudicated angiographic result with EmboTrap (within 3 passes).

5.2.2 **Primary Safety endpoint**

The primary safety endpoint will be measured as the confirmed occurrence of Symptomatic Intracerebral hemorrhage (sICH) within 24 hours (-8/+12 hrs) post-procedure, together with any other Serious Adverse Device Effects (excluding those already counted in sICH).

5.2.3 **Secondary endpoints**

For patients on whom rescue therapy was employed during the procedure, those secondary endpoints related to neurological outcomes observations will be removed from the data set as detailed in the protocol CIP003 rev 05 and these patients excluded from the main analysis of Good clinical outcome (mRS) and Neurological deterioration. This treatment will apply to the following secondary endpoints:

- **Good clinical outcome** – judged to be an mRS score of ≤2 at 90(+/-14) days.
- **Neurological deterioration** – defined by an increase of 4 points or more on the NIHSS score, at the 24-hour time point.

Sensitivity analysis will be performed to assess the robustness of results for these two endpoints to variations in how rescue therapy is defined to define the success of failure to reach an endpoint (Section 10.8).

For the statistical analysis of remaining secondary endpoints, rescue therapy will not be a consideration.

- **Procedure Time** – the time from groin puncture to final angiographic result.
- **Time to treat** - the time from angiographic visualization of large vessel occlusion to achievement of \geq mTICI 2b, or if not achieved, final angiogram. The number of passes to get to mTICI 2b or greater flow will also be recorded.
- **Mortality post-procedure** – All procedure-related mortality (i.e. directly traceable to a procedure- related SAE) at Day 7 post-procedure and all-cause mortality at 90(+/-7) days post-procedure.
- **Serious Adverse Device Effect (SADE)** – CEC confirmed that the EmboTrap device caused, or cannot be ruled out as having caused, an effect that has resulted in any of the consequences characteristic of a serious adverse event.
- **Procedure Related Serious Adverse Events (PRSAE)** – CEC confirmed that the interventional procedure caused, or cannot be ruled out as having caused, an effect that has resulted in any of the consequences characteristic of a serious adverse event.

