5.3 Other important Procedural data

The procedural success rate will be reported as follows:

The **overall procedural success rate** of the study is revascularization measured using modified Thrombolysis in Cerebrovascular Infarction (mTICI inclusive of the 2c rating). Successful achievement of procedural success is defined as achieving a mTICI score of 2b or greater, as assessed by the angiographic core laboratory, in the target vessel prior to the end of the procedure irrespective of the means or number of passes to achieve.

Procedural success using the EmboTrap device alone is the revascularization rate measured using modified Thrombolysis in Cerebrovascular Infarction (mTICI inclusive of the 2c rating). Successful achievement of EmboTrap procedural success is defined as angiographic core laboratory confirmation of a mTICI score of 2b or greater in the target vessel on the last pass of EmboTrap without rescue therapy.

5.4 *Source of Endpoint data and Derived variables*

All endpoint data are taken from the finally monitored data collected through the eCRF or in the case of safety endpoints as adjudicated by Clinical Events Committee and imaging endpoints as adjudicated by the core laboratory.

The primary efficacy endpoint of modified Thrombolysis in Cerebrovascular Infarction (mTICI inclusive of the 2c rating) will be extracted from the data provided by Imaging Core Laboratory Intrinsic imaging following all adjudications being completed in the Imaging consensus section of the eCRF.

Results recorded as TICI 2b, TICI 2c or TICI 3 , following 3 or less passes of the EmboTrap device, and without the use of rescue therapy, prior to taking the assessment angiogram (as defined in CIP002 rev 05) in the patient will be treated as having successfully achieved the primary endpoint. Results recorded as TICI 0, TICI 1 or TICI 2a will be treated as failures to achieve the primary endpoint.

The numerator used to calculate the primary safety endpoint will be calculated by summing the recorded occurrence of Symptomatic Intracerebral haemorrhage (sICH) within 24 hours (-8/+12 hrs) post-procedure, together with any Serious Adverse Device Effects (excluding those already counted in sICH) occurring.

A good clinical outcome will be judged to be an mRS score of ≤2 at 90(+/-14) days (mRS score range 0-6). Any subject recorded as having a score of 0, 1 or 2 at this timepoint will have successfully met the endpoint. Subject scores of 3 – 6 are considered fails.

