Procedure Time will be derived by calculating the time from when the groin was punctured until the acquisition time for the final post treatment confirmation of angiography result (i.e. the time from groin puncture to visualization/acquisition of the final angiographic result).

Time to Treat will be derived by calculating the time between the last time recorded for angiographic confirmation of the large vessel occlusion and the first time TICI 2b or greater was recorded angiographically, or if TICI 2b or greater was not achieved, the time of last angiographic acquisition.

Other sources of endpoint data are:

- All procedure-related mortality at day 7 post-procedure
- All-cause mortality at 90(+/-14) days post-procedure.
- Serious Adverse Device Effects (SADE).
- Procedure Related Serious Adverse Events (PRSAE).
- Symptomatic ICH (sICH).
- Neurological deterioration – defined by an increase of 4 points or more on the NIHSS, at the 24-hour time point.
- Evidence of Infarction of a previously uninvolved vascular territory, as evaluated from 24-hour imaging (CT/MRI).

A summary of all endpoints and the relevant outcome variables are listed in Table 1.

Table 1: Summary of endpoints and relevant outcomes

	Outcomes	Variable type	Notes
Primary Efficacy	mTICI	Binary	
 1. Value 1 = TICI 2b, TICI 2c or TICI 3 (favourable) achieved in the final Embotrap pass within 3 passes. 2. Value 0 = TICI 0, TICI 1 or TICI 2a (adverse) 3. All patients treated with Rescue therapy prior to taking of endpoint assessment angiogram count as fails.=0
Primary Safety	Symptomatic ICH (sICH) + Serious Adverse Device (SADE)	Binary	
 1. Occurrence of either (count only 1 per subject) 2. Within 24 hours (-8/+12 hrs) 3. Values: 1 = favourable, 0 = adverse
Secondary	Good clinical outcome	Binary	
 1. Judged to be an mRS score of ≤ 2 at 90(+/-14) days 2. Values 1 = favourable, 0 = adverse 3. Values for patients in whom rescue therapy was used will be excluded from the primary analysis 4.
	Procedure Time	Continuous (positive)	
 1. Defined as the time from groin puncture to visualization of the final angiographic result 2. Recorded in minutes. 3. No censoring of times 4. Lower value is more favourable

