	Time to treat		
 1. Defined as the time from angiographic visualization of large vessel occlusion to achievement of \geqmTICI 2b, or if not achieved, final angiogram. 2. Recorded in minutes. 3. No censoring of times 4. Lower value is more favourable
	All procedure-related mortality at day 7 post-procedure	Binary	Values: 1 = favourable, 0 = adverse
	All-cause mortality at 90 (+/-14) days post-procedure	Binary	Values: 1 =favourable, 0 = adverse
	Serious Adverse Device Effect (SADE)	Binary	
 1. The occurrence of any SADE in each patient. 2. Measured across 24 hours post-treatment. 3. Values 1 = favourable, 0 = adverse
	Procedure Related Serious Adverse Events (PRSAE)	Count	
 1. The number of PRSAEs (count) in each patient. 2. Lower value is more favourable
	Symptomatic ICH (sICH)	Binary	Values: 1 = favourable, 0 = adverse
	Neurological deterioration	Binary	
 1. Defined by an increase of 4 points or more on the NIHSS score, at the 24-hour time point 2. Values: 1 = favourable, 0 = adverse

	Outcomes	Variable type	Notes
			3. Values for patients in whom rescue therapy was used will be excluded from the primary analysis.
	Embolization to new territory (ENT)	Binary	1. Evaluated from Procedure Angiogram by core laboratory 2. Presence of ENT 3. Values: 1=absent, 0=present
	Evidence of Infarction of a previously unininvolved vascular territory	Binary	1. Evaluated from 24-hour imaging (CT/MRI) by the core laboratory 2. Presence of infarct in a vascular territory that was not involved or expected in the infarct to be treated 3. Values: 1=absent, 0=present
Procedural outcome data	mTICI	Binary	1. Value 1 = TICI 2b, TICI 2c or TICI 3 (favourable) 2. Value 0 = TICI 0, TICI 1 or TICI 2a (adverse)
Procedural outcome using only EmboTrap	mTICI	Binary	1. Value 1 = TICI 2b, TICI 2c or TICI 3 (favourable) using only EmboTrap and no other devices. 2. Value 0 = TICI 0, TICI 1 or TICI 2a (adverse) 3. All patients treated with rescue therapy will count as a fail

6 **Study Methods**

6.1 **General Study design and Plan**

The study is an open label, single arm study intended to generate a measure of the performance of EmboTrap for clearing and retrieving clots from large vessels causing strokes which can then be compared with a prespecified performance goal.

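### SAP 10.9 derives the primary safety endpoint as an uncapped sum with no time window for SADEs, whereas Table 1 and the planned analyses need a one-per-subject indicator; the SADE window is also inconsistent

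*SAP*

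**What the plan says.** The SAP describes the derivation of the primary safety endpoint in several places.

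- **SAP 5.4, Table 1, primary safety row.** The variable type is binary, and the notes read "Occurrence of either (count only 1 per subject) 2. Within 24 hours (-8/+12 hrs" (the 2 is the number of the second note). The coding is 1 = favourable, 0 = adverse.
- **SAP 10.9, item 1.** A rate for subject i is defined as sICH_i + (SADE_i − SADE_sICH(i)). The first term is "the number of occurrences subject 'i' has of Symptomatic Intracerebral hemorrhage", limited to 24 h (-8/+12). The second is "any other Serious Adverse Device Effects subject 'i' has", with no time limit. The third is the subject's SADEs already counted in the first term.
- **SAP 5.4, text.** "The numerator used to calculate the primary safety endpoint will be calculated by summing the recorded occurrence of Symptomatic Intracerebral haemorrhage", with the 24 h phrase placed on sICH, "together with any Serious Adverse Device Effects (excluding those already counted in sICH) occurring".
- **Protocol 3.1 and SAP 5.2.2.** The 24 h phrase follows sICH, and SADEs are then joined on. Protocol 3.1 has "together with any other Serious Adverse Device Effects (excluding those already counted in sICH" and SAP 5.2.2 has "within 24 hours (-8/+12 hrs) post-procedure, together with any other Serious Adverse Device Effects (excluding those already counted in sICH".

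For the secondary SADE endpoint, Table 1 says "Measured across 24 hours post-treatment", without the -8/+12 tolerance. Protocol 3.2 and SAP 5.2.3 give that endpoint no time limit. SAP 14.1 has adverse events recorded up to the 90-day follow-up.

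**The concern.** Two things differ between Table 1 and 10.9: the unit (a subject with an event, or a count of events) and the period over which SADEs count.

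On the unit, a programmer who follows the derivation section produces a variable that can exceed 1. Three planned outputs cannot take it: the proportions of subjects in subgroups (SAP 10.7), the Wilson binomial intervals (SAP 10.2) and the logistic models for poolability (SAP 13.3).

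On the window, SADEs after the first day are collected but enter the composite only under some of the passages.

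This is one of two primary endpoints. SAP 9.1 to 9.4 have it analysed in four populations: treated ITT, treated mITT, per protocol and Treated Set. In a single-arm study the rate is read directly, without a concurrent control counted by the same rule, so the counting rule should be fixed before analysis.

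**Working it through.** The documents give no expected rate, power or sample size for safety, so there is no planned figure to reproduce. The check applies each rule to the same subjects. Below, 1 means an event, the reverse of the Table 1 coding.

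**Step 1: the unit, one subject at a time (10.9 formula).**

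- An sICH in window that is not device-related, plus one separate SADE: 1 + (1 − 0) = 2. Table 1 gives 1. The result stays 2 even if each term is taken as 0/1, so the conflict does not depend on reading SADE_i as a count.
- A device-related sICH in window and nothing else. If SADE_i means all SADEs: 1 + (1 − 1) = 1. If SADE_i is taken literally as SADEs other than the sICH: 1 + (0 − 1) = 0, because the overlap is removed twice. Table 1 gives 1.

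**Step 2: the window.** The 24 h (-8/+12) window closes at 24 + 12 = 36 h. A non-sICH SADE on day 5 scores 0 under Table 1 if the note on the combined row applies to SADEs, and 0 + (1 − 0) = 1 under 10.9.

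**Step 3: illustration with four assumed subjects.** SADE_i is read as all SADEs.

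| Assumed subject | Table 1 | One per subject, no SADE window | 10.9 sum |
|---|---|---|---|
| Device-related sICH in window | 1 | 1 | 1 + (1 − 1) = 1 |
| Two non-sICH SADEs in window | 1 | 1 | 0 + (2 − 0) = 2 |
| One non-sICH SADE on day 5 | 0 | 1 | 0 + (1 − 0) = 1 |
| Device-related haemorrhage first found at 48 h | 0 | 1 | 0 + (1 − 0) = 1 |
| Total | 2 | 4 | 5 |

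With an assumed denominator of 176:

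- Table 1: 2/176 = 1.14% (Wilson 95% CI 0.31 to 4.05).
- One per subject, no SADE window: 4/176 = 2.27% (0.89 to 5.70).
- 10.9 sum: 5/176 = 2.84%. This is five events in four subjects, so no binomial interval applies.

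With 228 the three figures are 0.88%, 1.75% and 2.19%.

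**Step 4: size per subject.** 1/176 = 0.57 percentage points and 1/228 = 0.44. The 176 is the evaluable number for the efficacy test, and 228 is the enrolment ceiling, which includes roll-ins. Neither is the safety denominator, which is the number of treated ITT subjects (SAP 9.1). The two serve only as an assumed range. In a smaller population, such as mITT, each subject weighs more.

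**The case against.** The best defence is that the SAP largely settles the unit. Table 1 says binary and one per subject, and every planned analysis fits only that form. This stands. A reader might infer that the plan leaves open whether subjects or events are counted. It does not: the binary form is the only one that runs through the planned analyses. That makes 10.9 an error to correct, not an equal alternative.

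A reader might also count the 5.4 text as a second uncapped derivation. That does not follow. Table 1 sits in the same section, and summing a 0/1 variable over subjects is how a numerator is formed. On the unit, the conflict is with 10.9 alone.

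On the window, a reader might infer that protocol 3.1 and SAP 5.2.2 contradict Table 1. They do not. Their sentence can be read with the 24 h phrase covering sICH only or both components, and neither says that later SADEs count. The only explicit SADE windows are the two in Table 1, and both are 24 h. What remains is that Table 1 adds a limit that the definitions do not state and gives no reason for it, while 10.9 omits it.

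Nor do the documents support a 90-day window as the correct headline. SAP 14.1 sets the period for recording adverse events, not the window for this endpoint.

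Lastly, the consequence is limited. SAP 13.2 makes the endpoint descriptive, and SAP 14.2.1 still reports patients with at least one SADE, with no 24 h limit stated.

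**Conclusion.** The concern holds in this form. The 10.9 formula is wrong for an endpoint that Table 1 and the planned analyses treat as binary: it can give 2 for one subject and, read literally, 0 for a subject with a device-related sICH. Separately, the SADE window is 24 h (-8/+12) in the primary row of Table 1, 24 h in the secondary row, and unstated in protocol 3.1 and 3.2 and SAP 5.2.2, 5.2.3, 5.4 (text) and 10.9.

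Only the composite rate and its interval are affected. No hypothesis test, type I error, power or sample size depends on them. The effect is about 0.44 to 0.57 percentage points per reclassified subject, on an assumed treated denominator of 228 to 176. The total effect cannot be derived from the documents, because they give no expected number of late or repeated SADEs, and the four-subject example is invented to show direction only. The point should be fixed before analysis.

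**What to change.** 1. In SAP 10.9, replace the sum with one 0/1 indicator per subject: an event if there is a CEC-confirmed sICH within 24 h (-8/+12), or any CEC-confirmed SADE in the stated window, counted once. Delete the word *other* from the definition of SADE_i. Use the indicator in all four populations.
2. Make the 5.4 text refer to this indicator.
3. State one SADE window, with a reason, in identical words in 5.2.2, 5.4, both SADE rows of Table 1, and 10.9.
4. Because events are recorded to day 90, report the composite both ways: with SADEs within 24 h (-8/+12), and with SADEs over the full recording period. The sponsor names in advance which is the headline.
5. Say that the reported rate is the proportion coded 0 in Table 1, and report SADE event counts separately.

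The cost is SAP wording and one extra summary line. No new data, test or sample size is needed. The rate with the longer window may look less favourable than the 24 h rate.

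### SAP 10.9 takes sICH-linked SADEs out twice, so the primary safety score, if programmed literally, is 0 for a subject whose only event is a device-related sICH

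*SAP*

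**What the plan says.** SAP 10.9, item 1, is the only place where the primary safety endpoint is written as a subject-level formula: `sICH_i + (SADE_i − SADE_sICH(i))`. Its terms are defined as follows.

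- sICH_i is "the number of occurrences subject 'i' has of Symptomatic Intracerebral hemorrhage" in the 24-hour window, whether or not the device is implicated.
- SADE_i is "any other Serious Adverse Device Effects subject" i has.
- SADE_sICH(i) is the SADEs that the subject "has which are already counted in" sICH_i.

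Elsewhere the endpoint is given in words. SAP 5.2.2 takes sICH "together with any other Serious Adverse Device Effects (excluding those already counted in sICH"). SAP 5.4 builds the numerator from sICH "together with any Serious Adverse Device Effects (excluding those already counted in sICH) occurring", without the word *other*. Table 1 in SAP 5.4 makes the endpoint binary: a subject has an event if either component occurs, counted once. SAP 13.2 and protocol 8.3.3 describe the rate of sICH plus SADEs, with the overlap left out.

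SAP 13.2 reports the endpoint descriptively with a 95% confidence interval, which under SAP 10.2 is a Wilson interval for a binary variable. SAP 13.3 also fits logistic models to it to assess pooling across regions and sites.

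**The concern.** An sICH that the device caused, or may have caused, meets both definitions: it is an sICH and a SADE. The formula has to stop it being counted twice. One exclusion does that. SAP 10.9 applies two, one through the word *other* in the SADE_i label and one through the minus term. The second has nothing left to remove from SADE_i, so it cancels the sICH itself.

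The subjects affected are those whose only event is a bleed linked to the device. They would enter the primary safety analysis as event-free, while a subject with a bleed unrelated to the device would still count. Overlap is plausible: the SADE definition covers effects for which device causation cannot be excluded, and under protocol 12.1 the events committee rules both on whether a haemorrhage is symptomatic and on whether an SAE is attributable to the device.

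The derived variable goes into the safety rate and its interval in all four analysis cohorts (SAP 9.1 to 9.4), into the sex, device-length and product-code subgroups (SAP Table 3), and into the pooling models of SAP 13.3.

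**Working it through.** **Inputs.** For one subject, let s = number of sICH, d = SADEs that are already counted as sICH, and o = SADEs that are not. The formula and labels come from SAP 10.9, and the either/or rule from SAP Table 1. The documents state no safety rate, so there is no figure to reproduce.

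**Two readings of SADE_i.**

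- Literal label (SADE_i = o): score = s + (o − d).
- SADE_i as all SADEs (o + d): score = s + ((o + d) − d) = s + o.

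The literal score is lower by exactly d.

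| Subject's events | s | o | d | Literal label | SADE_i = all | Table 1 event |
|---|---|---|---|---|---|---|
| None | 0 | 0 | 0 | 0 | 0 | no |
| sICH, not device-related | 1 | 0 | 0 | 1 | 1 | yes |
| sICH, device-related | 1 | 0 | 1 | 1 + (0 − 1) = **0** | 1 + (1 − 1) = 1 | yes |
| One other SADE only | 0 | 1 | 0 | 1 | 1 | yes |
| Device-related sICH and one other SADE | 1 | 1 | 1 | 1 + (1 − 1) = 1 | 1 + (2 − 1) = 2 | yes |
| sICH not device-related and one other SADE | 1 | 1 | 0 | 2 | 2 | yes |
| Two other SADEs | 0 | 2 | 0 | 2 | 2 | yes |

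**What the table shows.**

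1. The yes/no result is wrong in one row: the lone device-related sICH. Capping at one per subject does not help, because the score is already 0.
2. With a device-related sICH plus another SADE, the literal score of 1 agrees with Table 1; only an uncapped sum would be short.
3. On either reading the score is a count that can exceed 1. A Wilson interval and a logistic model need a 0/1 outcome.
4. A negative score needs one bleed recorded as two SADEs: 1 + (0 − 2) = −1. Protocol 12.3.1 asks for a diagnosis rather than separate signs and symptoms, so this is a corner case.

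**Size, by assumption only.** Take 176 subjects (the planned evaluable sample). Each subject with a lone device-related sICH lowers the rate by 1/176 = 0.57 percentage points. Suppose 9 subjects have an sICH and 5 others have one separate SADE. The intended rate is (9 + 5)/176 = 14/176 = 8.0% (Wilson 95% CI 4.8% to 12.9%). Under literal coding:

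| sICH that are device-related (of 9) | Rate reported | Wilson 95% CI |
|---|---|---|
| 0 | 14/176 = 8.0% | 4.8% to 12.9% |
| 3 | 11/176 = 6.3% | 3.5% to 10.8% |
| 6 | 8/176 = 4.5% | 2.3% to 8.7% |
| 9 | 5/176 = 2.8% | 1.2% to 6.5% |

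The counts 9 and 5 and the device-related shares are invented to show the mechanism. They are not estimates for this trial.

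**The case against.** The strongest reply is that the formula transcribes the endpoint sentence term by term. SAP 5.2.2 also puts *any other* beside the exclusion in brackets, and nobody would read that sentence as deleting the sICH. The subtraction makes sense only if SADE_i means all SADEs; SAP 5.4 in fact says *any*, and SAP 13.2 simply says SADEs. Table 1 supplies a separate either/or rule that needs no subtraction, and under it a device-related bleed is an event. This all stands, and it settles the intent.

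A reader might therefore be tempted to infer that the plan treats device-related bleeds as non-events, or that the trial's safety rate is biased downward. The documents support neither. Every statement of the endpoint outside 10.9 keeps the bleed, and bias arises only if the program follows the 10.9 label against them. Nor do they support any percentage for the understatement, because they give no rate for sICH, for SADEs or for their overlap.

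It can also be said that the error would be caught. SAP 10.1 requires validation by an independent statistician or independent software, and sICH and SADE are each reported as secondary endpoints. This holds in part. A validator working from 10.9 could repeat the error. A comparison with the sICH rate exposes it only when the lone device-related bleeds outnumber the subjects with other SADEs. In the illustration above, the sICH rate is 9/176 = 5.1%: a composite of 4.5% would look impossible beside it, but one of 6.3% would not.

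Finally, the endpoint is descriptive and the confirmatory efficacy test does not use it. That is correct and limits the consequence. It does not cover the pooling models in SAP 13.3, which apply likelihood ratio tests at 0.15 to both primary endpoints.

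**Conclusion.** The concern holds as a wording error in one derivation. As defined in SAP 10.9, item 1, the formula gives 0 for a subject whose only event is a device-related sICH, where SAP 5.2.2, 5.4, Table 1 and 13.2 require one event. Literal programming would understate the primary safety rate by the number of such subjects divided by the number analysed. That number cannot be derived from the documents; it could be zero. The conclusion rests on reading *any other*, placed directly after the sICH term, as SADEs other than the sICH. If the label is instead taken to mean all SADEs, the overlap is removed correctly and only the mismatch between a count and Table 1's binary rule remains.

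It should be corrected because 10.9 is the SAP's only algebraic derivation of a primary endpoint, and the error would fall on the bleeds most relevant to the device.

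**What to change.** In SAP 10.9, item 1, make one of two changes:

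- define SADE_i as all SADEs of subject i and keep the subtraction; or
- keep the present label and delete the subtraction, leaving sICH_i + SADE_i.

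Then state the analysed variable directly: a subject has an event if there is an sICH or at least one SADE not counted as sICH, and otherwise has none. This follows the either/or rule of Table 1. It cannot miss a confirmed sICH, go negative or exceed 1, so it suits both the Wilson interval and the logistic models. State the coding as well, because Table 1 codes 1 as favourable while the 10.9 score rises with events. Whether the 24-hour window also applies to SADEs is a separate question that this change does not settle.

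The cost is one line of SAP text and the matching derivation code, with no new data. If the program already follows Table 1, no result changes. If it follows 10.9 literally and turns a positive score into an event, the rate can only rise or stay the same.
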